1.2 Objectives

- 1. Primary Objectives:
 - To assess the safety of the study devices through the collection of side effects throughout the study.
 - To assess efficacy by blinded evaluation of photography.
- 2. Secondary Objectives:
 - To assess of efficacy of the study device through Investigator and subject questionnaires.
 - To assess the ease of use of the new device.

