2.0 PROTOCOL

2.1 Protocol Methodology and Analysis

Methodology:

Subjects are to be enrolled in this clinical study if they are a healthy male or female 18 years of age or older. Up to 20 subjects will be enrolled at up to 1 study center. Subjects will attend a screening/pretreatment visit which may be performed on the same day as the treatment visit. Subjects may receive up to 5 treatments on multiple areas of the body such as, but not limited to, the face, legs, and arms. All subjects will be required to return a follow-up visit at 30 - 90 days after the final treatment in each treatment area. An unscheduled visit or phone call may be performed at any time during the study at the request of the subject or as deemed necessary by the site Investigator.

Analysis:

Upcoming generations are proving to have an interest in non-ablative aesthetic treatments and will drive demand for innovated products, procedures, and practice design. Due to this shift in patient base, practices need to evolve to adapt to the newer generational ideologies. This device uses the Alexandrite wavelength (755 nm) and the Nd:YAG wavelength (1064 nm) target hair follicles, unwanted veins, pigmented lesions and treat sun-damaged skin. Although this laser technology is one of the most used, there is a need for a new advanced treatment guidance system that is built into the laser.

Relevance:

According to the 2018 Plastic Surgery Statistics Report, the amount of laser treatments for minimally invasive aesthetic treatments have drastically increased over the past 8 years.² There is an increasing demand for new methods and novel laser technology for improved treatment outcomes. Other devices currently on the market cleared for use include, but are not limited to, the Excel and Candela devices.

Testability:

The Elite+ device, the most current approved Elite platform, had been previously cleared for use for hair reduction and the treatment of vascular lesions, benign pigmented lesions, pseudo folliculitis barbae, and wrinkles (FDA K141425). This study will utilize similar evaluation methods to assess prototype software and accessories.

Compatibility:

Although laser technology is a well-known and widely use technique for non-ablative aesthetic treatments, there is still a need to improve technology to reduce the number of treatments and provide a more effective treatment plan.

Predictive power:

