14.0 ADVERSE REACTIONS DEFINITIONS AND REPORTING REQUIREMENTS

All adverse events that occur, starting from the time of the first treatment, will be recorded in the source documents and Case Report Forms (CRF).

Adverse Events (AE) occurring will be captured and followed until the condition resolves, stabilizes, is otherwise explained, or the subject is lost to follow-up. Subjects will be instructed that they may contact the Investigator at any time throughout the course of the study.

The Investigator and/or designated study staff will review each event and assess its relationship to the study device (not related, unlikely, possible, probable, and highly probable). The following definitions will be used for rating relationship to the Elite iQ treatments:

- Not related The event is clearly related to other factors such as the subject's clinical state, therapeutic interventions, or concomitant medications administered to the subject.
- Unlikely The event was most likely produced by other factors such as the subject's clinical state, therapeutic interventions, or a concomitant medication administered to the subject; and does not follow a known response pattern to the investigational product.
- Possible The event follows a reasonable temporal sequence from the time of investigational product administration; **and/or** follows a known response pattern to the study sampling sessions; **but** could have been produced by other factors such as the subject's clinical state, therapeutic interventions, or concomitant medications administered to the subject.
- Probable The event follows a reasonable temporal sequence from the time of investigational product administration; **and** follows a known response pattern to the investigational product; **and** cannot be reasonably explained by other factors such as the subject's clinical state, therapeutic interventions, or concomitant medications administered to the subject.

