Highly Probable – The event follows a reasonable temporal sequence from the time of investigational product administration; and follows a known response pattern to the investigational product; and cannot be reasonably explained by other factors such as the subject's clinical state, therapeutic interventions, or concomitant medications administered to the subject; and either occurs immediately following investigational product administration, or improves on stopping the investigational product, or reappears on repeat exposure, or there is a positive reaction at the application site.

Each adverse event reported will be graded on a 3-point severity. Using the following definitions for rating severity will be used:

- Mild easily tolerated, causing minimal discomfort, and not interfering with normal everyday activities.
- Moderate sufficiently discomforting and may interfere with normal everyday activities.
- Severe incapacitating and/or preventing normal everyday activities.

A Serious Adverse Event (SAE) is any adverse device experience that results in any of the following outcomes: death, a life-threatening adverse device experience, in-patient hospitalization or prolongation of hospitalization, a persistent or significant disability/incapacity, or a congenital anomaly/birth defect. Important medical events that may or may not result in death, be life-threatening, or require hospitalization may be considered a serious adverse device experience when, based upon appropriate medical judgment, they may jeopardize the subject or subject may require medical or surgical intervention to prevent one of the outcomes listed in this definition

If any of the above adverse events are serious as defined by the FDA Code of Federal Regulations (CFR), Title 21, special procedures will be followed. All serious adverse events will be reported within 24 hours of acknowledgment to the Sponsor whether or not the serious events are deemed sampling session-related. All serious event reporting will adhere to 21 CFR part 812 and the IRB will be notified accordingly.

The SAE information will be entered into the database and a desk copy of the complete SAE report will be submitted to the study file.

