Adverse events, whether serious or non-serious, will be followed until the condition is resolved, stabilized, otherwise explained or the subject is lost to follow-up. Adverse events will be captured throughout the study and where appropriate, medical tests and examinations will be performed to document the resolution of event(s). Outcomes may be classified as resolved, improved, unchanged, worse, fatal, unknown or lost to follow-up. Following the resolution of any study-associated adverse events there will be no further adverse event reports for that subject.

Reporting Adverse Events:

Report Submit To Description/Constraints	
--	--

Adverse Events, Unanticipated Adverse Device Effect	IRB and Sponsor	If an unforeseen complication is determined to be an unanticipated adverse device effect, the investigator's report must be submitted within 10 working days after the investigator first learns of the effect.
Serious Adverse Events	IRB and Sponsor	The sponsor must be notified within 24 hours of serious adverse events. The IRB must be notified within 1 working day of serious adverse events as defined by FDA guidelines.

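### Section 14.0 ends adverse-event reports for a subject once study-associated events resolve, contradicting capture throughout the study; followed literally, later non-serious events of a different type could be missed

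*Combined protocol and SAP*

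**What the plan says.** The closing sentence of the adverse-event follow-up paragraph in Section 14.0 reads: "Following the resolution of any study-associated adverse events there will be no further adverse event reports for that subject".

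Other text on the same subject:

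- Same paragraph, first sentence: events "will be followed until the condition is resolved, stabilized, otherwise explained or the subject is lost to follow-up".
- Same paragraph, second sentence: "Adverse events will be captured throughout the study".
- Opening of Section 14.0: "All adverse events that occur, starting from the time of the first treatment, will be recorded".
- Section 14.0, severity grading: "Each adverse event reported will be graded on a 3-point severity".
- Section 1.2, a primary objective: "To assess the safety of the study devices through the collection of side effects throughout the study".
- Sections 2.8 and 2.9 require adverse events to be documented after treatment and at every follow-up visit. The schedule in Section 2.12 marks an adverse-event assessment at treatment visits and at follow-up.
- Section 2.15.6 bases the safety analysis on events collected over the whole study, summarised as the number and percentage of patients for each outcome.
- Section 2.1: subjects are "required to return a follow-up visit at 30 - 90 days after the final treatment in each treatment area".

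**The concern.** The closing sentence is a stopping rule for a subject, triggered by resolution of study-associated events. It has no end-of-study condition and is not confined to the event that resolved. A site cannot apply it literally and also capture events throughout the study.

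The trigger is an ordinary occurrence. Section 2.14 lists temporary redness, swelling and irritation, and hives that usually settle within hours. The same list includes outcomes that can last much longer, such as pigment change and hemosiderin staining. If an early transient reaction closes reports, a later event of a different, anticipated, non-serious type may never reach the summaries, and its percentage would be understated.

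Closure is by subject, but follow-up is required for each treatment area. A resolved reaction in one area could therefore close reports while another area is still being treated.

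Side effects are a primary objective, and Section 2.15.1 makes success depend partly on whether the physician finds the side-effect profile acceptable. That judgement needs a complete profile by event type.

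**Working it through.** The plan states no figure to reproduce. The check compares the texts and then works out the range from the visit schedule.

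**1. Can the sentence be read so that it agrees with the rest?**

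- *It ends follow-up of the resolved event.* The first sentence of the paragraph already does this ("will be followed until the condition is resolved, stabilized, otherwise explained or the subject is lost to follow-up"), and the closing words refer to the subject, not the event.
- *It ends submissions to the IRB and sponsor.* The sentence would then collide with the rules in Section 14.0 that all serious events go to the sponsor within 24 hours, and that unanticipated adverse device effects are reported within 10 working days. Neither rule has an exception for subjects whose earlier events have resolved. Section 14.0 also uses the word for the events that are graded ("Each adverse event reported will be graded on a 3-point severity"), so it is not reserved for outside submissions.
- *It applies only after the study ends.* The text does not say so.

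**2. Scheduled assessments after closure.** Inputs: n = 1 to 5 treatment visits and one follow-up visit (Section 2.12). Assessments per subject = n + 1. Worst case: a reaction at session 1 that resolves before the next visit, leaving n of n + 1 assessments after closure.

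| Sessions n | Assessments n + 1 | After closure | Share |
|---|---|---|---|
| 1 | 2 | 1 (follow-up only) | 50% |
| 2 | 3 | 2 | 67% |
| 3 | 4 | 3 | 75% |
| 4 | 5 | 4 | 80% |
| 5 | 6 | 5 (four sessions and follow-up) | 83% |

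If the sentence only ends follow-up of the same event, or outside submissions, the number affected is 0.

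**3. Time after closure, five sessions.** Inputs: sessions 2 to 10 weeks apart (Section 2.7) and follow-up 30 to 90 days after the last. Shortest: 4 × 14 + 30 = 86 days. Longest: 4 × 70 + 90 = 370 days.

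**4. Effect on a reported percentage.** Section 2.1 says: "Up to 20 subjects will be enrolled at up to 1 study center". One unreported subject changes an outcome's percentage by 1/20 = 5.0 points. If only 15 were treated (an assumption), it would be 1/15 = 6.7 points.

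**5. Illustration with assumed rates.** The documents give no event rates. Assume five sessions, independent risks per session pA (a common transient reaction) and pB (a different event type), and resolution before the next visit.

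- True proportion with type B = 1 − (1 − pB)^5. With pB = 5%: 1 − 0.95^5 = 22.6%, or 4.5 of 20.
- Proportion captured when reports stop after the first session with any event = pB(1 − r^5)/(1 − r), where r = (1 − pA)(1 − pB).

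| Assumed pA | r | Type B captured | Of 20 |
|---|---|---|---|
| 10% | 0.855 | 18.7% | 3.7 |
| 30% | 0.665 | 13.0% | 2.6 |
| 80% | 0.190 | 6.2% | 1.2 |

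These figures show direction and range only. The percentage with any event does not change, because closure requires that a first event was already reported.

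**The case against.** The strongest defence is that the protocol mostly separates data capture from reporting. Events are recorded, captured or documented in the case report forms, and Section 2.14 treats regulatory reporting as a separate step. The disputed sentence speaks of reports and stands directly before a table of submissions to the IRB and sponsor. On that reading, case report form data continue and the safety summaries are intact. Redundancy with the first sentence proves little, because Section 14.0 repeats itself elsewhere. The literal reading is also applied selectively: if the explicit rules for serious events survive the sentence, the equally unconditional rule to record all events from first treatment should survive it too. The worst case further needs site staff to set aside a visit schedule that still calls for assessment.

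Much of this stands as a limit on the consequence. The 50% to 83% is a share of scheduled assessments, not of events lost, and the range starts at 0. No safety comparison is planned, and Section 2.15.1 sets no numeric safety threshold, so no test or decision rule changes. Photographs and sponsor review of documented events make complete loss less likely. Both safeguards are partial: Section 2.13 has photographs at all visits, but Sections 2.6 and 2.8 make them optional before later sessions and after treatment, and sponsor review reaches only events that were documented.

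The defence does not remove the contradiction. As shown above, the submissions reading conflicts with the unconditional submission rules in the same section, and nothing in the text tells a site which reading to follow.

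**Conclusion.** The concern holds. The sentence contradicts capture throughout the study, and on its face it permits under-reporting on a primary objective. It should be corrected, though its reach is limited.

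The events exposed are mainly later, non-serious, anticipated ones of a type not yet reported for that subject. Recurrences of the same type would also be cut off, which could affect severity and duration but not the patient-level percentages. The bounds rest on one follow-up visit per subject. The upper bound further assumes a literal reading and a first-session reaction that resolves before the next visit. That the wording is contradictory is certain; how many events would be missed cannot be estimated from the documents.

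**What to change.** Delete the sentence. Alternatively, confine it to the period after the subject's final study visit, once ongoing study-associated events have resolved or stabilised. If the second option is used, reconcile it with Section 2.14, which requires follow-up to resolution and does not mention stabilisation.

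The cost is a one-sentence amendment, with the written IRB approval that Section 21.0 requires. Assessment is already scheduled at every treatment and follow-up visit, so no visit or procedure is added. The one downside for the sponsor is that some outcome percentages may be higher, by 5 points for each subject of 20 whose event would otherwise have gone unreported.

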15.0 PROTOCOL DEVIATIONS

All requests for protocol deviations by the Investigator must be communicated to the sponsor in writing and if accepted by the Sponsor must be approved by the IRB. If a deviation occurs, the Investigator must inform the Sponsor as soon as possible. The Sponsor will notify the IRB in accordance with IRB specific policies.

16.0 CONFIDENTIALITY AND DISCLOSURE OF MEDICAL INFORMATION

As part of this study the Investigator and the team at the research facility will keep records of subject participation in the study. These study records will include personal information that the subjects provide including age, sex, etc., the results of the study, information about response to treatments, photographs taken during the study and other medical information relating to participation in the study.

Under federal law the study records cannot be used or disclosed by the Investigator for research purposes unless subjects sign the informed consent authorization.

Some or all of the test results, photographs and other information will be reported to Cynosure, LLC, the manufacturer of the test device (Sponsor), and consultants that are helping conduct the study. The Sponsor and its consultants will analyze and evaluate these results and information and may report them to the U.S. Food Administration and the FDA, Institutional Review Board or other regulatory agencies in the United States and/or foreign countries. The subject's study records will be assigned a code number by the study team and they will ordinarily not be identified by name in the study records that are sent to the Sponsor and its consultants. However, The Sponsor, the Institutional Review Board and its consultants will have the right to see the complete study records, including the subject's name, and might choose to do so. If reports or articles are written about the study, the subject will not be identified by name in them however your study information and photographs may be used.

The research facility will review and use the study records only for purposes of this study. They will keep the subject's identity confidential and, except for the disclosures described above, will not disclose the study records to other parties unless disclosure is required by law. Once the research facility discloses information in the study records, photographs or medical records to the Sponsor or

its consultants, the information will no longer be protected by federal law. Because of the need to release information to these parties, absolute confidentiality cannot be guaranteed. However, the Sponsor and its consultants will only use information for purposes of the study and will not disclose your study records to parties other than; the FDA or other regulatory agencies in the United States and/or foreign countries, unless disclosure is required by law. If reports or articles are written about the study, subjects will not be identified by name in them however, subject study information and photographs may be used.

Study records will be kept at the research facility according to applicable regulations and policies and may be kept indefinitely following the completion of the study. Subjects will not have the right to review their records while the research is in progress. However, they will be able to review their records after the research has been completed.

17.0 CLINICAL RESEARCH CONDUCT

The study will be conducted in accordance with the protocol, International Conference on Harmonization (ICH) GCP guidelines, applicable regulations and guidelines governing clinical study conduct and ethical principles that have their origin in the Declaration of Helsinki. The investigator must ensure that the study is conducted in accordance with the provisions as stated in the FDA regulations and complies with the applicable local or regional regulatory requirements.

18.0 REPORTING FOR THE STUDY

A study summary report will be generated. It will include a description of the clinical conduct of the study and results.

Study Summary Reporting:

Report	Submit To	Description/Constraints
Deviation from Investigational Plan	IRB and Sponsor	A deviation performed in an emergency to protect the life or physical well-being of a patient necessitates notification of the IRB and sponsor. The Investigator's report must be submitted within 5 working days after the emergency occurred. Deviations in a non-emergency situation require notification to sponsor prior to implementation
Failure to Obtain Informed Consent	IRB and Sponsor	The Investigator must make notification within 5 working days after device use, using the Protocol Deviation CRF. The report must include a brief description of the circumstances justifying the failure to obtain informed consent.
Final Report	IRB and Sponsor	The Investigator must submit a final report within 3 months after termination or completion of the investigation.

Withdrawal of IRB approval	Sponsor	The Investigator must report a withdrawal of the reviewing IRB approval within 5 working days .
Progress Report	IRB, Monitor and Sponsor	The Investigator must submit progress reports at regular intervals, and as required by the IRB, but in no event less than annually.

19.0 DISCLOSURE

The Principal Investigator and Cynosure employees and consultants have signed confidentiality agreements with the sponsor. This confidentiality agreement ensures that all information provided to the Investigator or Data Management and Statistics group dealing with the study and information obtained during the study will be regarded as confidential.

20.0 RESPONSIBILITY OF THE INVESTIGATOR

The Investigator is responsible for ensuring that the clinical study is performed in accordance with the International Conference on Harmonization (ICH), Good Clinical Practice (GCP) guidance E6, FDA Good Clinical Practice Regulations, Declaration of Helsinki (DoH) and the Health Human Service (HHS) Belmont Study. Investigators will supply information to the sponsor such that the sponsor can comply with the Financial Disclosure Rules.

21.0 PROCEDURE FOR AMMENDMENTS TO PROTOCOL

No deviations from this protocol will be permitted, except in a medical emergency, without the approval of the Sponsor. Any amendment to this study will be discussed by the Investigator and the Sponsor. If agreement is reached concerning the need for modification, this will be made in a formal amendment to the protocol.

All revisions and/or amendments to the protocol must be approved in writing by the appropriate Institutional Review Board.

22.0 TERMINATION OF STUDY

The Sponsor reserves the right to discontinue this study for administrative reasons at any time. The Investigator reserves the right to discontinue the study for safety reasons at any time in collaboration with the Sponsor.

23.0 DATA SECURITY

To ensure the privacy and confidentiality of data for this protocol, the data will be stored on a restricted access location on a company server. Access to the project directory containing the data will be limited to the Investigators and research staff. Information about data security awareness is promoted through user training and education, supplemented by policies and procedures. Password protection will be used for all transactions that allow viewing, editing, and analysis of data, or that provide access to data fields derived from the original source documents.

